#### Phone call (day 30 $\pm$ 1 day)

During this phone call the following evaluations will take place:

- Safety assessment by AE / ADE / DD collection

#### **3.7.3 Case Report Form**

The Case Report Form (CRF) of the study will be filled by investigator. The CRO will insert the data in the EDC

All data collected through CRO's EDC system will be checked for completeness and extreme values (outliers) presence. Any anomaly will be forwarded by the statistician/data manager to the Investigator and/or Clinical Research Associates. Such data queries will be solved with priority, in no more than 3 days from the query's opening. The statistician decides to use/accept the revised data for the subsequent statistical analyses.

Because of legal considerations (GDPR directive effective from 21.05.2018 in all European Union countries), patients or their legal surrogates may have an absolute right to request that their data are removed from the study database. As a result, there are potentially two datasets: the full list of enrolled patients, and the list containing the patients who have kept their data available. The latter is obtained after deleting the data for patients who withheld or withdrew their consent and did not allow their data to be submitted or maintained in the database. Only the latter dataset can be used in the analysis.

It is the CROs responsibility to keep all the above-mentioned software tools to their latest and most secure versions.

Data is stored according to existing legislation and current regulation (Directive 2001/20/EC and EU Regulation 1924/2006), and with the rules of Good Clinical Practice ICH E6 (R2). Succinctly, the Investigator Study File contains, among other study documents, the eCRFs printouts. The Sponsor will archive all the electronically collected data on DVDs. A copy of the eCRF printouts will be provided to the participating centres.

The collected data will be subjected to multiple checks for correctness (entry errors). Every information will be verified by an SDV (Source Data Verification) process, performed by the study monitors. Data Clarification Forms will be implemented to obtain clean data.

## **4. DATA MANAGEMENT AND ANALYSIS**

---

### **4.1. Record keeping and archiving**

At the end of the trial, all copies of all essential documentation will be archived securely by the Investigator for a minimum of 10 years starting when the last device has been put on the market. Essential documents are those which enable both the conduct of the trial and the quality of the data produced to be evaluated and show whether the site complied with all applicable regulatory requirements. Included in the records to be maintained are the signed protocol Trial, signed consent forms, ethics committee approval letters, correspondence with Sponsor/CRO and any other documents to identify the patients.

The CRO will notify the sites when the trial documentation can be archived. All archived documents must continue to be available for inspection by competent authorities or Sponsor audit upon request. In addition, if the Investigator moves/retires, etc., he/she should provide the Sponsor with the name and address of the person who will look after and be responsible for the trial-related records.

### **4.2. DATA MANAGEMENT**

#### **4.2.1. Data review, DB cleaning, issuing, and resolving queries**

The Data Management process includes all activities related to data handling regarding:

- Set-up of study-specific DB for data processing and analysis.
- Supporting the Data entry / Data editing.
- Export of data to R statistical software.
- Creation of post-entry checks and listings.
- Clean-file process.

CRO will be responsible for all these activities. The confidentiality of records that could identify patients will be protected, respecting the privacy and confidentiality rules in accordance with the applicable regulatory requirement(s).

#### **4.2.2. Procedures for data retention and retention period definition**

Electronic/physical data (study documents) will be retained by the Sponsor or other contracted third party for a minimum of 10 years starting when the last device has been put on the market, as required by clinical trial legislation.

### **4.3. STATISTICAL ANALYSIS**

#### **4.3.1. Sample size calculation**

The Short Health Scale for Haemorrhoidal Disease (SHSHD), the primary outcome of this clinical investigation, was used as the basis for the calculation of the required sample size. In a study published by Renato Pietroletti et al. (2022) (7), the researchers assessed the performance of a rectal ointment based on Zn-L-carnosine in the

treatment of haemorrhoidal disease by using the SHSHD following 4 weeks of treatment with the medical device.

Their results showed an SHSHD mean  $\pm$  SD score of  $7.90 \pm 4.17$  before treatment and  $4.05 \pm 0.22$  after 4 weeks of treatment with Proctilor® rectal ointment.

Lacking the results of a similar emulsion (PROCTOeze® PLUS) we assumed a mean  $\pm$  SD SHSHD score of  $6.20 \pm 0.25$  after 4 weeks of treatment for the haemorrhoidal disease, resulting in a moderate effect size of around 0.42.

By employing a one-tailed Wilcoxon signed-rank test for matched pairs at a significant level of 2.5 % and a power of 80 % we derived a sample size of 50 evaluable patients to prove PROCTOeze® PLUS performance.

Considering a possible screen failure rate of 10% we require 55 enrollable patients.

In addition, 5 patients should account for a possible 10% moderate drop-out rate, so 60 patients should be screened for enrolment in the clinical investigation.

The software used in the calculation was G\*Power v3.1.9.7 (8).

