### 3.3.3. Patient identification

Each patient enrolled will be identified by the patient number, a five digits code (e.g., 01.001), which will be the only identification element and will be used only for the purposes of this study. This code will consist of the Centre number (e.g., 01/02/etc. corresponding to each Centre) and of the sequence number of the patient (e.g., .001, which means the 1st patient enrolled). If the patient is declared a screening failure (one or more eligibility criteria is not fulfilled and the patient cannot participate in the study), the identification code will not be reassigned to another patient.

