### **3.3.4. Patient Enrolment and allocation**

Once the eligibility is established according to inclusion/exclusion criteria, ICF signed, patients will be enrolled

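### The two 10% allowances are added to 50 rather than divided out, so screening 60 is expected to yield about 48.6 evaluable patients, not 50

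*Combined protocol and SAP*

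**What the plan says.** Section 4.3.1 (Sample size calculation) of the protocol bases the calculation on a "one-tailed Wilcoxon signed-rank test for matched pairs at a significant level of 2.5 % and a power of 80" per cent, with assumed scores "resulting in a moderate effect size of around 0.42". From this, "we derived a sample size of 50 evaluable patients to prove PROCTOeze" PLUS performance. Two allowances follow. The first reads "Considering a possible screen failure rate of 10% we require 55 enrollable patients". The second reads "In addition, 5 patients should account for a possible 10% moderate drop-out rate", and it leads to the conclusion "so 60 patients should be screened for enrolment in the clinical investigation". The same chain of 50, 55 and 60 stands in the protocol synopsis (Sample size calculation) and in the report summary (Sample Size Calculation and Statistical Methods).

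Two other sections fix the sequence of events. Section 3.3.3 describes a screening failure as a case where "one or more eligibility criteria is not fulfilled and the patient cannot participate in the study". Section 3.3.4 says "Once the eligibility is established according to inclusion/exclusion criteria, ICF signed, patients will be enrolled". Screen failure is therefore a loss before enrolment, and drop-out a loss after it.

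**The concern.** The screening target has one purpose: to leave 50 evaluable patients after the losses the plan itself expects. Each loss is a proportion of the patients who enter that stage, so the target has to be divided by the proportion retained. Adding 10% of the final number for each loss gives too small an allowance, because the patients added to cover one loss are themselves exposed to loss.

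The steps are also labelled the wrong way round. The screen-failure rate is used to go from evaluable to enrollable patients, and the drop-out rate to go from there to the number screened.

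What is at stake is a stated sample-size figure, repeated in three places, that does not deliver the number it is meant to protect.

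**Working it through.** **Inputs (section 4.3.1).** Evaluable target 50; screen-failure rate 10%; drop-out rate 10%; stated enrollable 55; stated screened 60; effect size about 0.42; one-sided alpha 2.5%; power 80%.

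**Step 1: reproduce the plan's figure.** 50 + 0.10 x 50 = 55, then 55 + 0.10 x 50 = 60. This matches exactly, so both allowances are 10% of 50, added on. Compounding instead would give 50 x 1.1 x 1.1 = 60.5, which rounds up to 61.

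**Step 2: run the stated rates forward from 60.**
- Enrolled: 60 x 0.90 = 54, already below the stated 55.
- Evaluable: 54 x 0.90 = 48.6, which is 1.4 (2.8%) below 50.
- Even if 55 were enrolled, 55 x 0.90 = 49.5.

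Sixty leads to 50 through 55 only if 5/60 = 8.3% fail screening and 5/55 = 9.1% drop out.

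**Step 3: divide the losses out.**
- Enrolled: 50/0.90 = 55.6, so 56.
- Screened, in one step: 50/(0.90 x 0.90) = 50/0.81 = 61.7, so 62.
- Screened, rounding up at each step: 56/0.90 = 62.2, so 63.

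Check: 62 x 0.81 = 50.2 and 63 x 0.81 = 51.0.

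**Step 4: does the order matter?** No. 0.90 x 0.90 = 0.81 whichever loss comes first, and 50 + 5 + 5 = 60 whichever allowance is added first. The reversed order affects only what the intermediate 55 is called.

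**Step 5: chance of reaching 50.** If each screened patient independently ends up evaluable with probability 0.81 (an assumption), the binomial probability of at least 50 evaluable is about 0.40 for 60 screened, 0.60 for 62 and 0.70 for 63.

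**Step 6: power at the expected yield.** The documents do not give the distribution of the differences. For a normal parent, the signed-rank test behaves like a t test on m = N x 3/pi patients, so power = 1 - F(t(0.975, m - 1)), where F is the noncentral t distribution function with m - 1 degrees of freedom and noncentrality 0.42 x sqrt(m).

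| Evaluable N | Power, normal parent (ARE 3/pi) | Power, minimum ARE (0.864) |
|---|---|---|
| 48 | 79.5% | 75.2% |
| 48.6 | 80.0% | 75.7% |
| 49 | 80.3% | 76.1% |
| 50 | 81.1% | 77.0% |

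Under the normal parent, 49 patients are enough for 80%, so the stated 50 has one patient of slack. With a logistic parent, power is about 85% at 48 and 86% at 50.

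The effect size depends on a pre/post correlation that the plan does not state. With the assumed means and SDs, (7.90 - 6.20)/sqrt(4.17^2 + 0.25^2 - 2 x r x 4.17 x 0.25) is 0.407 at r = 0, 0.420 at r = 0.5 and 0.425 at r = 0.7.

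**The case against.** The strongest case on the other side has four parts.

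- **Ten per cent could mean 10% of the 50 evaluable patients.** Then 60 would be consistent with itself. That is not the usual meaning of a screen-failure or drop-out rate, and the text defines no other denominator, so this does not rescue the figure.
- **The gap is within the uncertainty of the inputs.** The rates are called possible, and 8.3% and 9.1% are hard to tell from 10%. Lowering the effect size from 0.42 to 0.41 costs 1.9 points of power at 50 patients, more than the 1.6 points between 48 and 50. This stands, and it is why the point is minor.
- **The target is set elsewhere.** The synopsis (Number of patients) and sections 3.3 and 3.3.5 all define the population as 50 evaluable patients. The 60 is a number that should be screened; nothing makes it a cap or a stopping point. This also stands.
- **The trial is finished.** The statistical report gives 50 enrolled and analyses 50 (34 females, 16 males). This removes any urgency. It does not validate the 60, since the sections available do not give the number screened.

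A reader might infer that the plan loses its 80% power. The figures do not support that. Power is about 80.0% at the expected yield of 48.6, and drops to 79.5% only if the yield is rounded down to 48. A reader might also take the reversed order of the two allowances for a second numerical error. It is not one, because the factors commute.

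**Conclusion.** The concern holds as an arithmetic slip. Under the plan's own rates, taken in their usual sense, 60 screened patients are expected to give 48.6 evaluable, not 50. The figures that match the rates are 56 enrolled and 62 screened, or 63 with rounding at each step, against the stated 55 and 60.

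The shortfall comes entirely from adding instead of dividing. The order of the two allowances is a labelling fault. Planned power is met to rounding, given an effect size of 0.42 and a normal parent; other parents move the level of power far more than the 1.4 missing patients do. No analysis or conclusion of the trial changes.

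**What to change.** Correct the text in section 4.3.1, the protocol synopsis and the report summary in one of two ways:

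1. Restate the targets: 50 evaluable / 0.90 = 56 enrolled (10% drop-out), and 50 / 0.81 = 62 screened (10% screen failure as well), or 63 if each step is rounded up. State which rounding is used.
2. Keep 60 screened, and say that it is expected to yield about 48 to 49 evaluable patients, with power still about 80% at effect size 0.42 under a normal parent distribution.

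Either way, attach the drop-out allowance to the step between evaluable and enrolled, and the screen-failure allowance to the step between enrolled and screened. The cost is a few sentences in three places, with no change to trial conduct or analysis.

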#### **4.3.2. Statistical design, method, and analytical procedures**

Design: Open, non-comparative, multicentre, prospective, interventional trial.

The principle of intention-to-treat (ITT), as far as practically possible, will be the main strategy of the analysis adopted for the primary endpoint and all the secondary endpoints. These analyses will be conducted on all participants.

No imputations will be made on missing data.

The statistical plan details the following 3 analysis sets which will be evaluated in this study:

- The ITT population, which includes each patient enrolled in the study that used at least one dose of the investigational product and had at least one efficacy assessment.
- The Per-Protocol population, which excludes patients with major protocol deviations or violations (e.g., did not use the investigational product, did not attend all the visits, or had missing data regarding the primary endpoint) and includes those with valid observations on the primary endpoint.
- Safety population, which includes each patient enrolled in the study that used at least one dose of the investigational product.

The protocol outlines that a two-sided p-value of 0.05 or less will be used to declare statistical significance for all analyses. Similarly, all confidence intervals will be calculated at the 95% level.

No adjustment for multiplicity will be made to adjust the type 1 error rate for secondary endpoints. If necessary, relevant results from other studies already reported in the literature will be considered in the interpretation of results.

If a patient is missing information for one or more variables, the missing data will not be replaced.

All statistical analyses will be performed using the R statistical software v 4.2.2 (9), or the latest stable version at the time of statistical analysis.

The final analysis will be completed after all patients have been exited from the study, all queries have been resolved, and the database has been locked.

The overall type I error rate will be preserved at 5%. All tests will be two-sided. Data from unscheduled visits will not be included in the analysis.

Statistical analyses will be conducted on all patients who have successfully completed the study without a protocol deviation that is regarded as impacting the assessment of the key variables (as per protocol). The quality and completeness of the collected data will be evaluated preliminarily compared to data analysis. If a patient is missing information for one or more variables, even after the resolution of its query, the missing data will not be replaced. If a patient has been involved in violation of inclusion/exclusion criteria, the respective data will be excluded from the analysis. Quantitative variables (i.e., demographic) if normally distributed will be described through mean, and standard deviation (SD); non-normally distributed variables will be described using median and range of interquartile. The Student's t-test and the Mann-Whitney U will be employed to perform comparative analysis in accordance with the distribution of these variables. Factorial variance analysis can also be used to evaluate any interactions between quantitative variables and linear progression models to relate possible confounding bias with independent variables.

Categorical variables will be finally described using frequencies and percentages and comparative analysis will use the  $\chi^2$  test.

The safety analysis will be done on the safety population.

Minor deviations from the original statistical plan (SAP) will be considered acceptable (e.g., due to the non-parametrical form of the data, statistical tests will be adjusted accordingly). Major deviations from the SAP will be reported by the statistician to the Clinical Project Manager and will result in clinical trial protocol amendments.

Tables will include baseline characteristics of the participants, medical history and concomitant medications, and safety outcomes. A CONSORT diagram illustrating the flow of patients through the study is also planned.

Additional details about statistical analysis will be documented in the Statistical Analysis Plan (SAP), enclosed in the Trial Master File.

## **5. DEVIATIONS FROM THE PROTOCOL**

The investigator is not allowed to deviate from the Protocol, except if the deviation affects the patient's rights, safety and well-being, or the scientific integrity of the trial.

Generally, any deviation from the protocol must be verified, reported and analysed by the Investigator and the Sponsor and, immediately after, communicated to the EC. The Investigator will not apply this statement under emergency circumstances (20,21).

All spontaneous protocol deviations shall be recorded and reported to the Sponsor. Deviations shall be also reported to the regulatory authorities if required by national regulations. All deviations will be included, as required, in the study report (SR).

## **6 TERMINATION OF THE STUDY**

---

### **6.1. END OF THE TRIAL AND ITS DURATION**

The end of trial will be estimated in 8 months from the site activation.

### **6.2. PREMATURE TERMINATION/SUSPENSION OF THE TRIAL**

The Sponsor may stop this trial in a Centre for any of the following reasons:

- the Centre cannot include an adequate number of patients.
- Serious and/or persistent non-compliance with the protocol.
- Careless or premeditated false documentation in the trial documentation.
- Inadequate cooperation with the CRO and/or Centre.
- Non-compliance with GCP or Competent Authority (CA) or EC requirements.
- The Investigator asks to discontinue the trial.
- Lack of confidentiality.

If the trial is prematurely terminated or suspended for any reason:

- the patients will be informed promptly by the Investigator, and the EC and Regulatory Authorities will be notified.
- The Sponsor shall remain responsible for providing resources to fulfil the obligations from the protocol and existing agreements for following up with the patients enrolled in the clinical investigation.

## **7. COMPLIANCE TO ETHICS AND REGULATORY**

---

### **7.1. GUIDELINE AND LEGISLATION**

The protocol of the present trial is developed in accordance with ICH Harmonized Tripartite guidelines for GCP requirements and Local Romanian legislation.

### **7.2. ETHICS COMMITTEE APPROVAL**

Prior to the initiation of the trial, the Investigator must submit all the documents requested by each centre EC for review and approval. The Investigator, and any other member of the team, if also a member of the EC, must not participate in the decision-making. A signed and dated letter identifying the members of the EC reviewing this protocol will be requested.

### **7.3. INFORMED CONSENT AND PATIENT INFORMATION**

The Investigator is responsible for and will obtain the signed consent form from each patient in the trial. As this is not a clinical trial only data protection consent will be used as requested by GDPR legislation. All patients invited to participate in the trial are entitled to make their decision based on all currently available information provided to them by the Investigator/designee. In addition, they will be given the Data Privacy Sheet (DPS) a document in Romanian language, written in clear and concise lay language for review and consideration. These documents must have been previously approved by the relevant EC and may further be updated as new important information becomes available that may affect the patient's willingness to participate or continue in the trial.

The patients must be made aware that they can refuse to join the trial or can withdraw their consent at any time without prejudicing further medical care. The contact details of the Investigator (telephone no, etc.) will be provided. The patients must also know that their personal records may be reviewed in confidence by the

Sponsor's staff or representatives and by the authorities and that personal information will be collected and retained in a confidential database. Conditions for ensuring the anonymity of data and the security and confidentiality of the database will be explained.

Consent will always be given in writing after the patient had had adequate time to review the information and ask questions. The patient and the Investigator conducting the informed consent discussion will both personally write the name, sign and date these consent forms. Two copies of the data privacy consent form shall be signed. The Investigator shall provide one signed copy of the signed data privacy consent and one copy of the data privacy sheet to the patient and retain the second copies of the signed forms in the onsite study file. The forms will be reviewed by CRO personnel.

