Objectives	This trial aims to evaluate the overall performance and safety of the MD PROCTOeze® PLUS in relieving symptomatology of haemorrhoidal disease and

	
anal irritation in adult patients affected by Grade I-II (Goligher classification) haemorrhoids as assessed by the patient and the Investigator at the end of the treatment period.
 
The primary objective is the assessment of performance by the improvement in the quality of life (QoL).
 
Secondary objectives are the assessment of performance by validated scales completed by the Investigator and by the patient at the end of the treatment period.
 
The safety of the MD will be evaluated through Adverse Events (AE) and Adverse Device Effect (ADE) incidence assessed by Investigators and reported according to the current legislation.

Outcomes	
Primary outcome
 
 
• The Short Health Scale for Haemorrhoidal Disease (SHSHD) (5) will be used to evaluate the QoL. The questionnaire will be completed by the patient at baseline and day 30, at the end of the treatment with the MD.
 
 
Secondary outcomes
 
 
• The Haemorrhoid Severity Score (HSS) (6), a physician-reported outcome, will be completed by Investigator at baseline and day 30, at the end of the treatment with the MD.
 
• The Haemorrhoidal Disease Symptom Score (HDSS) (5), a patient-reported outcome questionnaire, will be administered by Investigator to each patient at baseline and at day 30, at the end of the treatment with the MD.
 
• Evaluation of AE, SAE, ADE, SADE, ASADE, USADE incidence assessed by Investigator and reported according to the current legislation for the whole study period. DD will be also evaluated.
 

Design	Open, non-comparative, prospective, interventional trial.
Disease	Hemoroidal disease :Grade I – II symptomatic haemorrhoids (according to Goligher classification)
Population	Adult patients affected by Grade I-II (Goligher classification) haemorrhoids that did not need hospitalization and treated as outpatients (the treatment will be self-administered at home).

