### **3.1. DESIGN**

Open, non-comparative, multicentre, prospective, interventional trial.

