### 3.3.1. Inclusion criteria

Patients will be eligible for inclusion if **ALL** the following criteria are respected:

- Men and women  $\geq$  18 years old.
- Patients diagnosed with Grade I – II symptomatic haemorrhoids (according to Goligher classification) confirmed by clinical and anoscopic or proctoscopic examination performed within 3 months before baseline.
- Patients able to do self-administration at home of the MD, for 30 days, to treat symptoms of haemorrhoids and anal irritation.
- Patient free from the following treatments for haemorrhoids for at least 4 weeks: laser treatments for haemorrhoids, steroid or non-steroidal anti-inflammatory drugs, analgesics, any anti-haemorrhoidal treatment, anticoagulants, and antiplatelet agents.
- Patients able to communicate adequately with the Investigator and understand the questionnaire.
- Patients able to understand and who can provide valid informed consent to the trial.

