### 3.7.2.1. Study visits

#### Visit 1 Screening / Baseline Visit (day 0)

At each Centre, patients will be enrolled consecutively. During this visit, patients who will meet the eligibility criteria (inclusion and exclusion criteria) will be enrolled after the signature of the informed consent form and will be informed verbally and in writing about the nature and requirements of the trial. Patients agreeing with the participation in the study will have to date and sign the informed consent form prior to any study-related procedure. All the screening procedures must be completed during this visit.

During this visit, the Investigator will collect information regarding medical history, demography, concomitant treatments and medications, AE/SAE if applicable. The Investigator will report data on the appropriate eCRF pages.

A physical examination will be performed, including evaluations of vital signs; pulse, blood pressure (diastolic and systolic), weight / height and BMI (kg/m^2) data will be collected. An evaluation of the haemorrhoidal disease will be performed, and a confirmation of the diagnosis and of the stage of haemorrhoids will take place, according to inclusion criteria (patients diagnosed with Grade I – II symptomatic haemorrhoids (according to Goligher classification, confirmed by clinical and anoscopic or proctoscopic examination performed within 3 months before baseline)

During this visit the following questionnaires will have to be completed:

- **HR-QoL questionnaire: SHSHD (by patient)**
- **HSS (by Investigator)**
- **HDSS (by patient)**

During this visit, the MD will be provided to each patient. The used, partially used and unused containers of the MD will have to be brought back to the centre on the last study visit. The MD will be supplied in the same package available on the market, and with the same leaflet / IFU – Instructions for Use.

A patient diary will be supplied; it will have to be completed at home by patients for the whole duration of the study. A series of information will have to be collected related to the health status of the patient (not an exhaustive list): use of any treatment or OTC or prescribed medications (concomitant treatments and medications), start and stop dates and name/dosage of the product will be collected; AE/ADE/DD occurrence; self-administration of the MD (according to IFU and standard clinical practice).

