### 3. INCLUSION EXCLUSION CRITERIA

#### 3.1. INFORMED CONSENT

Has the subject freely signed the written informed consent?	Yes  No 
---	--

Please note:

written informed consent must be given before any study specific procedures take place.

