## 8. END OF STUDY

Please mark **only the primary reason**. Reasons other than **Study Completed** require explanation

- 1  Study completed
- 2  AE/SAE (complete AE & SAE form, if applicable)
- 3  Non-compliant participant
- 4  Withdraw consent
- 5  Failure to meet inclusion/exclusion criteria
- 6  Other

Explanation

*I am confident that the information supplied in this case record form is complete and accurate data. I confirm that the study was conducted in accordance with the protocol and any protocol amendments and that written informed consent was obtained prior to the study.*

Investigator's Signature:

Date of signature:

d	d	m	m	y	y	y	y
---	---	---	---	---	---	---	---

Note

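### Section 7.3 denies that this is a clinical trial and limits consent to data protection, which conflicts with the interventional design and with the informed consent the protocol and CRF require

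*Combined protocol and SAP*

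**What the plan says.** Section 7.3 of the protocol is the section devoted to consent. It contains the sentence "As this is not a clinical trial only data protection consent will be used as requested by GDPR legislation". The steps that follow, on duplicate signature, the copy for the patient and the copy for the site file, name the data privacy consent form and the data privacy sheet and no other document.

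Elsewhere the same protocol says:

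- Section 3.1 (Design): "Open, non-comparative, multicentre, prospective, interventional trial". The synopsis describes the same interventional design, and section 4.3.2 repeats it.
- Section 3.3.1 includes among the inclusion criteria: "Patients able to understand and who can provide valid informed consent to the trial".
- Section 3.3.4 makes signature a condition of entry: "ICF signed, patients will be enrolled".
- Section 3.7.2.1, Visit 1: "Patients agreeing with the participation in the study will have to date and sign the informed consent form prior to any study-related procedure".
- CRF section 3.1 notes that "written informed consent must be given before any study specific procedures take place". In CRF section 8 the investigator signs that "written informed consent was obtained prior to the study".
- Section 7.6 commits the study to the Declaration of Helsinki and GCP. Item 26 of the Declaration, reproduced in Annex 5, requires that subjects be told about aims, methods, benefits and risks.

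**The concern.** Two statements in one sentence of section 7.3 are at odds with the rest of the protocol: that the study is not a clinical trial, and that data-protection consent is therefore the only consent used. The first is a premise and the second a rule drawn from it.

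Patients in this study accept more than the processing of their data. They receive a device to use at home, are barred from analgesics, anti-inflammatory drugs, anticoagulants and antiplatelet agents for the duration (section 3.4.2), and undergo physical examinations and questionnaires at scheduled visits. A privacy form is not designed to explain these matters or their risks. What is at stake is whether the protocol tells sites clearly which consent to obtain. It also matters for reading the CRF: if section 7.3 is taken at its word, it is unclear which document a yes to the informed-consent question refers to.

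**Working it through.** No arithmetic applies: the point depends on no alpha, power, effect size, standard deviation or patient number. The check is a comparison of texts in three steps.

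**1. The premise that this is not a clinical trial.** The synopsis, section 3.1 and section 4.3.2 all call the study an interventional trial. Section 4.3.1 calls it a clinical investigation, and the closing part of section 4.3.2 speaks of amendments to the clinical trial protocol. Section 7.3 is alone in denying it.

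**2. The rule that only data-protection consent is used.**

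| Place | Consent required |
|---|---|
| Section 7.3, sentence at issue | Data protection only |
| Section 7.3, copying and filing steps | Data privacy consent and data privacy sheet |
| Section 3.3.4 | Informed consent form signed before enrolment |
| Section 3.7.2.1, Visit 1 | Informed consent form signed before any study procedure |
| Both schedules of assessments | Informed consent at Visit 1 |
| Section 3.6.2 | Adverse event recording starts from informed consent |
| CRF section 3.1 | Written informed consent before study-specific procedures |
| CRF section 8 | Investigator attests that written informed consent was obtained |

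The synopsis and section 1.5.6 also give the CRO the task of preparing an informed consent form, and the dossier's table of contents lists that form as its own section 8. The protocol therefore plainly expects such a form to exist. The restriction in section 7.3 excludes it.

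**3. Section 7.3 against itself.** The section opens by making the investigator responsible for a signed consent form from each patient in the trial. It says patients decide on the basis of all available information, presents the privacy sheet as something given in addition, grants a right to decline to join, refers to a discussion of informed consent, and speaks of consent forms in the plural. These phrases imply consent to participation. The restricting sentence and the copying steps point the other way. Nowhere does the section name an informed consent form for participation as a document to be signed, copied and filed.

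The result is that both halves of the sentence conflict with several other places, and the section is not consistent internally.

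**The case against.** The strongest reply is that the operating instructions already get this right. A site working from Visit 1, the schedule of assessments and the CRF has to obtain informed consent, record it and attest to it. Section 7.3 itself contains enough participation wording that it is not a clear order to enrol on a privacy form alone. This stands, and it limits the point to a contradiction in the text. It does not remove the contradiction, because the restricting sentence sits in the section a site or ethics committee would consult on consent.

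A second reply is that the study is over: the summary gives 16 January 2025 as the end of treatment and 3 April 2025 as the date of the final report. This also stands in part. Rewording now cannot change what anyone signed, although a check of the site files can still establish it.

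A reader might infer more than the documents support:

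- **That all 50 patients took part without participation consent.** The consent form pages were not available for review, and the CRF asks about informed consent for each patient. No failure is shown.
- **That a patient who signed only a privacy form was ineligible, so that the data would be removed and the results lose validity.** The criterion in section 3.3.1 concerns the ability to give valid consent. Signature is a separate condition in section 3.3.4 and a separate CRF item, outside the inclusion list. The removal rule in section 4.3.2 applies to violations of inclusion or exclusion criteria, and the same section also names intention-to-treat as the main strategy. The documents do not show that any data would be excluded.
- **That patients underwent a washout on a privacy form.** No washout is scheduled. Patients must already be free of the listed treatments for at least 4 weeks, and all screening takes place on day 0.

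**Conclusion.** The concern holds as a contradiction in the protocol text. The sentence in section 7.3 is wrong as written: its premise conflicts with the stated design, and its rule conflicts with the enrolment condition, the Visit 1 procedure, the CRF item and attestation, the Helsinki and GCP commitment, and other wording in section 7.3. It should be corrected because it bears on participant protection and the correction is cheap.

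Its size cannot be expressed as a number of affected patients. The sentence applies in principle to everyone enrolled, but how many patients, if any, signed only a privacy form cannot be known from these documents. The sample size, alpha, P values and analysis are unaffected. The conclusion rests only on the wording of the protocol and CRF and makes no assumption about what happened at the sites.

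**What to change.** 1. Delete the restricting sentence from section 7.3.
2. State there that each patient signs the informed consent form for participation and, separately, the data privacy consent, both before any study procedure. Extend the copying and filing steps to cover both forms.
3. As enrolment is complete, confirm from the site files which forms each of the 50 patients signed, and when, and report the result in the study report. This is the step that still has practical value.

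The cost is the rewording of one section and a check of 50 patients' consent records at three centres. The dossier already lists an informed consent form, so no new form should be needed. No analysis has to be rerun.
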